## **5. Participant Selection:**

*Stroke patients:* For SAs # 1-2, subjects will be adult females and males, ages 40-80 years with (1) one cerebral ischemic infarction < 1 month affecting the primary motor output system of the hand at a cortical (M1) level as defined by MRI of the brain, (2) paresis of the hand for more than 3 days after their cerebral infarction ( $MRC \leq 4$ - of wrist- and finger extension/flexion movements), (3) extension of the wrist ( $MRC \geq 3$ , > 10 degree) at the time of the enrollment into the study, (3) no other neurological disorders, (4) no aphasia that prevents subjects from following instructions or their inability to communicate effectively with the study team, (5) no or only mild cognitive impairment but not to the level of dementia (RBANS(Randolph et al. 1998)), (6) no or only mild depression (Hamilton Depression score of <19) (7) no contraindication to TMS or MRI, (8) no intake of CNS active drugs that blocks plasticity (9) the ability to give informed consent. We have chosen this age range because stroke is a disease of elderly people. Only 8.9% of ischemic strokes affect people under the age of 50 years(Fonarow et al. 2010). As plastic changes are likely age-dependent (Sawaki et al. 2003), we would like to exclude “age” as a possible confounding factor by matching our patients post-stroke to the healthy controls (data gathered under R56 NS070879-01) thereby avoiding the possibility that older age may result in a false negative result in our stroke patients.

**Healthy Subjects:** We will study 30 healthy adult females and males, ages 40- 80 years with no neurological or psychiatric diseases and a normal neurological examination, normal MRI of the brain and normal neuropsychological testing(Randolph et al. 1998), no intake of CNS active drugs, no contraindication to TMS and ability to give informed consent.

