#### **4. Study design and Methods:**

The measurements and interventions described will be obtained at 2 time points in all patients (1 and 6 months post stroke). The data will be compared to the results of healthy age matched controls to establish abnormalities

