#### **4.4. Studies pertaining to Specific Aim #2: *Determine the role of contralesional M1 in motor performance during the post stroke recovery process***

In two studies (Study 1 and 2) we will test the effect of contralesional M1 transcranial magnetic stimulation on the subject's performance in a manual pointing task (4 different level of complexity, Presentation®) using either the paretic or the non-paretic hand in a counterbalanced randomized order and measures of motor excitability (IHI, SICI, MT, SRC, see above for details). To accomplish the goal of each study, a total of 6 experiments will be conducted in a randomized counterbalanced order. In Study 3 we will implement prediction and classification models to determine the predictive roles of variables measured in specific aim 1 on the supportive/detrimental role of cl\_M1 derived

from the effect of M1 downregulation by rTMS (Specific aim 2, study#1).

Study #1: Role of cl\_M1 on motor performance. In all subjects, we will test the effect of 1 Hz rTMS and sham cl\_M1 stimulation on the subject's performance in a pointing task of increasing difficulty using either the paretic or the non-paretic hand in a counterbalanced randomized order. Specifically, as previously described by our group in detail (Butefisch et al. 2003; Butefisch et al. 2008) rTMS at 90% MT will be used to decrease cl\_M1 function using a rapid Magstim (Magstim Company, UK). Briefly, coil position will be monitored online using Brainsight. EMG activity will be recorded from the ECU and other control muscles with the settings already detailed in Specific Aim 1. After determining the MT in the ECU hot spot (Rossini et al. 1994b), rTMS will be applied through the air-cooled figure-of-eight coil at 90% MT and 1 Hz frequency for 15 min (Butefisch et al. 2009). The effects will be compared to Sham stimulation applied at similar intensity and frequency (Butefisch et al. 2009). An additional two visits will be conducted for healthy subjects that include a repeat of the study measures described in specific aim 1 but we will stimulate at 80% rTMS to explore the effects compared to 90% rTMS and these visits will take the standard amount of time of 2-3 hours per visit. Preliminary data demonstrated different effects of different intensities and this needs to be confirmed in this population.

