Study #2: Effect of transient disruption of cl\_M1 on M1 excitability and IHI. In all subjects, we will test the effect of cl\_M1 stimulation on the outcomes of MT, SRC, SICE and IHI in both motor cortices one month post stroke. All measurement will be repeated 6

months after infarction. The data will be compared to the results of healthy age matched controls to establish abnormality.

*Statistical analysis:* The statistical tests performed in this section will mirror those in the specific aim 1 with the addition of repeated measures factors specifying acquisition time (pre- or post-rTMS stimulation) and time post-stroke (1 and 6 months). The mixed-models will investigate the effect of cl\_M1 stimulation on TMS outcomes MT, SRC, SICE, rHI over time post-stroke. Additionally, we will use the mixed model to assess the effects of cl\_M1 excitability (SICE from SA #1) and cl\_M1 activation (number of activated voxels and % signal change within ROI) on rTMS-related changes in TMS measures.

Study #3: Identify biomarkers in the subacute and chronic phase of stroke that predict either the supportive or detrimental role of contralesional M1 as determined by responses to specific intervention protocols. In this study, we will implement prediction and classification models to determine the predictive roles of variables in SA #1 on the supportive/detrimental role of cl\_M1 derived from the effect of M1 downregulation by rTMS (SA#2, study#1). Specifically, we will train (and test) a binary classifier to predict subjects' responses (positive or negative) to rTMS (down regulation and sham) at 1 and 6 months post-stroke based on sets of predictors defined by SAs # 1 & 2. The association between the set of predictors and the binary response will be established during an iterative cross-validation process involving training and testing, in which different data are used to establish a predictive model and to evaluate its performance. We will assess performance using standard measures of prediction accuracy such as sensitivity,

specificity, positive predictive value, and negative predictive value. We will employ and compare multiple modeling techniques such as the Elastic Net, logistic classifier, and Bayes classifiers. Developing and optimizing the classifiers will identify subsets of measures that have the greatest predictive power for forecasting the role of cl\_M1.

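### Time since stroke is modelled only as a nominal 1- or 6-month level, although late enrolment and a multi-session block let the actual day differ between patients

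*Combined protocol and SAP*

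**What the plan says.** All references are to the combined protocol and SAP.

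- **Entry (section 5).** The infarct criterion is "one cerebral ischemic infarction < 1 month affecting the primary motor output system of the hand". A practical lower limit follows from requiring "paresis of the hand for more than 3 days after their cerebral infarction". Wrist extension must be present "at the time of the enrollment into the study".
- **Assessment times (section 4).** Measurements and interventions "will be obtained at 2 time points in all patients (1 and 6 months post stroke"). The statistical paragraph under Study #2 in section 4.4 treats time as a repeated-measures factor, "time post-stroke (1 and 6 months").
- **Content of a time point.** Section 4.1.1 places motor-task practice no later than the day before fMRI. Section 4.1.4 uses the MRI to navigate the TMS, then lists the excitability and mapping measures. Section 4.4 says that "a total of 6 experiments will be conducted in a randomized counterbalanced order", which can mean 6 in all or 6 for each of Studies 1 and 2. The same section gives 2 to 3 hours as the standard visit length.
- **Windows.** The Motor Activity Log phone calls in section 4.1 have week ranges and a one-week contact window. Laboratory and imaging visits have none.
- **Covariates.** The Aim 1 models in section 4.3 contain subject type, hemisphere and stimulus factors, with no time term. Section 4.4 adds pre/post acquisition, time post-stroke, and contralesional M1 excitability and activation. Actual days since stroke is named neither as a covariate nor as a Study #3 predictor.

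**The concern.** The 1-month assessment cannot be a single day, and enrolment can close only just before it is due. A patient enrolled in the first week can have the block arranged around day 30. A patient enrolled in the last days before 1 month cannot, because practice, imaging and the experiments all still have to follow. Both patients carry the same time label in the analysis.

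This matters because recovery over time is what the study investigates. If excitability changes over the first weeks, differences in measurement day add unexplained variation between patients. If measurement day is also related to damage, part of a recovery-time effect could be read as an effect of damage. The wrist-extension rule offers a possible route, since a patient who regains extension late can enter only late.

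**Working it through.** The plan states no figure on visit timing, so there is none to reproduce. The arithmetic below only shows what the text permits.

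**Inputs from the documents:** enrolment before 1 month; paresis for more than 3 days, so day 4 is taken as the earliest entry; one practice day before fMRI; 6 experiments.

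**Assumed:** 1 month = day 30; a gap *g* of 1, 2, 3.5 or 7 days between visits; no separate visit for the Aim 1 TMS measures.

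**Block length:** L = 1 + 6*g*. Three ways of scheduling are all compatible with the text:

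| Gap *g* (days) | L (days) | A: start at entry (day 4 to 30) | B: all held to day 30 | C: block centred on day 30 | L/2 (days) |
|---|---|---|---|---|---|
| 1 | 7 | day 4 to 37 | day 30 to 37 | day 26.5 to 33.5 | 3.5 |
| 2 | 13 | day 4 to 43 | day 30 to 43 | day 23.5 to 36.5 | 6.5 |
| 3.5 | 22 | day 4 to 52 | day 30 to 52 | day 19 to 41 | 11 |
| 7 | 43 | day 4 to 73 | day 30 to 73 | day 8.5 to 51.5 | 21.5 |

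If the 6 experiments apply to each study (12 in all), L = 1 + 12*g*, or 13 to 85 days.

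**Spread between patients**

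- Rule A: with entry uniform over days 4 to 30, the SD of start day is 26/√12 = 7.5 days.
- Rule B: the SD of start day is 0.
- Rule C: early entrants' blocks have their midpoint at day 30. A late entrant who cannot start before about day 30 has a midpoint of 30 + L/2, a difference of L/2. At gaps of 2 and 3.5 days that is 6.5 and 11 days. The two visits are about 5 × 30 = 150 days apart, so the difference is 6.5/150 = 4% to 11/150 = 7% of that interval.

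**Link to severity.** In a linear model that omits measurement day, the spurious standardised slope on severity is corr(severity, day) × standardised effect of day. Assumed correlations of 0.3 to 0.7 and day effects of 0.2 to 0.5 give 0.3 × 0.2 = 0.06 up to 0.7 × 0.5 = 0.35. The result is 0 if the correlation is 0 or every patient is measured on the same day. The documents supply neither input, so this range is no estimate. The written mixed models also contain no damage coefficient to which it would apply.

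**Which analyses are exposed**

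- *Between patients:* stroke versus control; effects of contralesional M1 excitability and activation on the rTMS response; the Study #3 classifier. Differences in day enter these directly.
- *Within patients:* 1 Hz versus sham, and pre versus post rTMS. Each patient is his or her own comparison, and the randomised counterbalanced order keeps post-stroke day from lining up with condition.

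**The case against.** The strongest reply is that the limit in section 5 governs enrolment, while sections 4 and 4.4 fix measurement at 1 month. Nothing says that testing begins at enrolment. If every patient were held to day 30, start days would not differ and no link with severity could arise. That is correct, but the plan contains no such rule. Where staff simply aim for 1 month, a late entrant is still measured later than an early one.

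A reader might infer that time since stroke varies widely and tracks severity. The documents do not support either as fact. The text leaves the spread unbounded without showing that it is large, and comparing a late entrant's whole block with an early entrant's nominal day 30 would overstate it, because both need the same block. The documents report no association between enrolment day and damage, and late entry can have other causes. Section 3 also measures damage by the response to TMS, lesion volume and tract asymmetry as well as by the quality of wrist and finger extension, so the entry rule is not the damage measure itself.

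A reader might also count the randomised order of experiments as part of the problem. It is a safeguard for the treatment contrasts.

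**Conclusion.** The point holds in a limited form. The plan neither limits nor adjusts for actual days since stroke within its nominal visits, and the entry rule together with the multi-session block makes some difference between patients likely unless a common start day is imposed. On assumed gaps of 2 to 3.5 days, early and late entrants would differ by about 6.5 to 11 days in the midpoint of the block. The difference is zero under a common start on day 30 and larger if testing starts at enrolment. Any relation to severity is plausible but unreported, and no bias figure can be drawn from the documents. The between-patient analyses are affected; the sham and pre/post contrasts largely are not. The change is worth making because it is cheap and concerns the axis that the study sets out to examine.

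**What to change.** 1. In the mixed models of sections 4.3 and 4.4, keep the nominal visit factor where it is used and add actual days since stroke at the session. Centre it within the 1-month and 6-month visits and set it to zero for healthy controls, who have no stroke date. Its coefficient is then estimated from patients only, and the stroke-versus-control contrast refers to a patient at the average day of the visit.
2. Add the same variable to the Study #3 candidate predictors.
3. Record the date of every session. Section 4.1 uses the stroke date to schedule calls, but the plan does not say that session dates are kept.
4. In section 4, state the permitted day range for each block, and repeat the analyses without sessions that fall outside it. The range is for the sponsor to choose.

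The cost is 1 df per model and slightly wider intervals if days since stroke proves unrelated to outcome. No visit is added and no eligibility rule changes.

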#### 4.3. TMS data analysis:

Peak to peak MEP amplitudes will be measured off-line. Recordings with EMG background activity will be excluded from further analysis. Data analysis SICE, SRC, rIHI, aIHI, and mapping: Peak to peak MEP amplitudes will be measured off-line. Recordings with EMG background activity will be excluded from further analysis. For

the SRC, the mean MEP amplitudes at each stimulus intensity will be calculated. For SICE, rIHI and aIHI, mean MEP amplitudes elicited at different ISIs and CS intensities will be calculated as a percentage of the mean test MEP amplitude evoked by TS alone. CS intensities will be expressed as percentage of the subject's MT. For mapping, the area will be calculated as the number of stimulation sites that produce an MEP in of the trials. The center of gravity (CoG), an estimate of the center of the map, will be calculated for each target muscle (ECU or FCU) based on the weighted MEP amplitudes at each active location. Statistical analysis: We will use linear mixed models to quantify the effects of subject type (cortical stroke patient, subcortical stroke patient, healthy control) along with other, measure-specific factors (outlined below) on outcomes of interest. The analyses will incorporate models of within-subject correlations stemming from multiple measures on each subject. Hypothesis testing will be conducted on mean model parameters at a significance level  $\alpha = 0.05$ . Post-hoc analysis will be corrected for multiple comparisons. For SICE: A mixed model will assess the effect of subject type and stimulated hemisphere (ipsi- or contralesional for the stroke subjects, zero for the controls) along with repeated measure CS intensity (60%, 80% MT) on relative conditioned MEP amplitude. For rIHI: A mixed model will be used to determine the dependence of relative conditioned MEP amplitude on subject type along with the repeated measures inhibition (cl\_M1 on il\_M1 and il\_M1 on cl\_M1) and ISI (2ms, 10ms). For aIHI: We will perform a mixed model analysis to determine the dependence of relative conditioned MEP amplitude on subject type along with the repeated measures inhibition (as above), time after go signal (0ms, 300ms, 400ms, and 450ms), and target size (small, extra-large). For SRC: The effect of the repeated measure stimulus intensity on the average MEP

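### Age is named as a possible confounder and handled by matching, but no mixed model comparing subject types includes age or the matched set; the main expected cost is precision

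*Combined protocol and SAP*

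**What the plan says.** Section 5 (Participant Selection) gives the reason for controlling age, "As plastic changes are likely age-dependent", and the means: "matching our patients post-stroke to the healthy controls (data gathered under R56 NS070879-01". Section 4 repeats the intention: "The data will be compared to the results of healthy age matched controls to establish abnormalities". Section 4.4, Study 2, says the same. Patients and controls share an eligibility range of 40 to 80 years. No caliper, ratio, or choice between individual and frequency matching is stated.

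The analysis is in Section 4.3: "We will use linear mixed models to quantify the effects of subject type (cortical stroke patient, subcortical stroke patient, healthy control", followed by factors specific to each measure. Section 4.4 carries the same models into Aim 2, adding acquisition time (before or after rTMS) and time since stroke. Section 6 only refers back to these sections.

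On where the controls come from, Section 5 cites data gathered under another grant but also says "We will study 30 healthy adult females and males, ages 40- 80 years". Section 4.4 adds "An additional two visits will be conducted for healthy subjects".

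**The concern.** The plan raises age as a threat to the patient-control comparison and then leaves it out of the models that make the comparison. Two things follow. First, if age is related to an outcome, its variance stays in the between-subject error, so between-group main effects are estimated less precisely than the data allow. Second, if matching leaves a difference in mean age, nothing in the analysis removes it.

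The second point also applies inside the patient group. Subject type has three levels. Matching patients to controls does not by itself balance cortical against subcortical patients.

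**Working it through.** **1. Terms listed for each model (Sections 4.3 and 4.4)**

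| Model | Terms | Age or matched set |
|---|---|---|
| SICE | subject type, hemisphere, CS intensity | none |
| rIHI | subject type, direction of inhibition, ISI | none |
| aIHI | subject type, direction, time after go signal, target size | none |
| SRC | subject type, hemisphere, stimulus intensity | none |
| MT, mapping | subject type, hemisphere | none |
| Aim 2 | as Aim 1, plus pre/post rTMS and 1 v 6 months | none |

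**2. Which contrasts are touched**

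Write b for the age slope of an outcome. A between-group main effect carries b × (gap in mean age). A difference between two levels of a repeated factor in the same subject does not, because b × age cancels. So additive age effects drop out of within-subject contrasts and of group-by-repeated-factor contrasts. They do not drop out if the slope differs by occasion: the group difference in pre/post change then carries (b_post − b_pre) × gap.

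**3. Inputs for size**

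The documents give no power, effect size, SD or number of patients, so there is no planned figure to reproduce. What follows is illustrative.

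- Stated: 30 controls, ages 40-80, alpha 0.05.
- Assumed: 30 patients, a two-sided test, one measurement per subject, outcome SD 1, age-outcome correlation ρ of 0.2, 0.3 or 0.5.
- Assumed: ages uniform on 40-80, so age SD = 40/√12 = 11.55 years.

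**4. Precision, with ages balanced**

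SE = √(1/30 + 1/30) = 0.258 unadjusted; adjusting for age multiplies it by √(1 − ρ²). Power = Φ(d / SE − 1.96). For d = 0.5 without adjustment: 0.5/0.258 − 1.96 = −0.02, which gives 49.1%.

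| | Unadjusted | ρ = 0.2 | ρ = 0.3 | ρ = 0.5 |
|---|---|---|---|---|
| Between-subject variance removed (ρ²) | – | 4% | 9% | 25% |
| Power, 0.5 SD, 30 patients | 49.1% | 50.7% | 52.8% | 60.9% |
| Power, 0.8 SD, 30 patients | 87.3% | 88.5% | 90.1% | 94.7% |
| Power, 0.5 SD, 15 patients | 35.2% | 36.5% | 38.1% | 44.7% |
| Power, 0.5 SD, 60 patients | 60.9% | 62.6% | 65.0% | 73.3% |
| n per group, 80% power, 0.5 SD | 63 | 61 | 58 | 48 |

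**5. Bias, if matching leaves a gap**

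Bias in outcome SD = ρ × gap / 11.55. Type I error = P(|Z + bias/SE| > 1.96), at 30 v 30.

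| Residual gap | Bias at ρ = 0.2 / 0.3 / 0.5 | Type I error |
|---|---|---|
| 0 years | 0 / 0 / 0 | 5.0% throughout |
| 2 years | 0.03 / 0.05 / 0.09 | 5.2% / 5.5% / 6.3% |
| 5 years | 0.09 / 0.13 / 0.22 | 6.3% / 7.9% / 13.4% |

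**6. How large a gap is plausible**

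With no matching at all, and both groups drawn from the same age distribution, the SE of the gap at 30 v 30 is 11.55 × √(2/30) = 2.98 years, so 95% of gaps fall within ±1.96 × 2.98 = ±5.8 years. With 15 or 60 patients the limits are ±7.2 and ±5.1. The 5-year row is therefore close to what unmatched groups would show at the extreme. Working matching should do better.

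**The case against.** The strongest reply is that age is already handled, by design. Matching is a legitimate control for confounding. If it is close, the bias is near zero and leaving age out of the model mainly costs precision. That stands, and it rules out several stronger readings.

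- **That the group contrasts are biased by age.** A reader might infer this from the missing covariate. The documents show no imbalance. Residual bias depends on the quality of the matching, which they do not describe.
- **That every group contrast is affected.** Many planned terms are within-subject, and an additive age effect cancels there (step 2).
- **That the controls are purely a separate, existing cohort, matched only at group level.** The grant citation suggests existing data, but the future-tense plan to study 30 healthy adults and their additional visits point the other way. Nothing says the matching is group-level.

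The assumed inputs are also open to challenge. No document gives an age-outcome correlation. Section 5 speaks of plasticity, not of resting measures such as MT or map area. A uniform age distribution puts 10/40 = 25% of patients under 50, whereas Section 5 cites 8.9% of ischemic strokes below that age. At ρ = 0.2 and a 2-year gap the effect is negligible.

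What survives is the omission itself. The plan considers age important enough to match on, gives no rule from which the closeness of the match could be judged, and leaves age out of all the models that compare subject types.

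**Conclusion.** The point holds in limited form. No model containing subject type includes age or a matched-set term. Age variance stays in the error of between-group main effects, and any imbalance left by matching, including between cortical and subcortical patients, is uncorrected.

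Lost precision is the expected cost: modest at ρ of 0.2 or 0.3, and material at 0.5 (about 12 percentage points of power for a 0.5 SD difference at 30 v 30). Bias is a risk and has not been shown. It is small for a 2-year gap and would matter mainly if matching achieved little and age were strongly related to the outcome.

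These sizes rest on the assumed patient number, age SD and correlation, and on one measurement per subject. The omission can be read directly from Sections 4.3 and 4.4. The conclusion is the same whether the controls are existing or newly studied.

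**What to change.** Keep the matching. In Sections 4.3 and 4.4, prespecify age (continuous, centred) as a fixed covariate in every mixed model that contains subject type. In the Aim 2 pre/post-rTMS models, also include an age-by-acquisition-time term: the plan's stated worry is age-dependent plasticity, which concerns change, and a main effect of age alone would not address it.

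State the matching rule and the source of the controls. Add a matched-set term only if matching is individual. With three subject types, 30 controls and no stated ratio, it may not apply. Report age by subject type for each analysed set, so that the closeness of the match can be seen.

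The model change costs one or two sentences and one or two degrees of freedom per model. Eligibility and matching already require age, so no new data are needed.
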